6.2.2.4 Early Study Drug Discontinuation Assessment

If the subject discontinues the study drug prior to the Week 48 Visit, the subject will be asked to return to the clinic within 5 days of stopping study drug for the Early Study Drug Discontinuation Visit. Every attempt should be made to keep the subject in the study and continue to perform the required follow ups and procedures through to the Week 48 Visit (see Section 6.2.2.3). If this is not acceptable to the subject or investigator, the subject may be withdrawn from the study.

If the subject discontinues the study drug and without notifying the Investigator within 5 days, the subject may be withdrawn from the study, at the Investigator's discretion.

At the Early Study Discontinuation Visit, any evaluations showing abnormal results indicating that there is a possible or probable causal relationship with the study drug will be repeated weekly (or as often as deemed prudent by the Investigator) until the abnormality is resolved/returns to baseline (based on Day 1 Visit) or is otherwise explained.

The following will be completed:

- Review/record of SAE/AE's and changes in concomitant medications
- Obtain measurements of blood pressure, pulse, temperature, height and weight
- Complete or symptom directed physical exam, as clinically indicated
- Obtain blood and urine samples as described in section 6.2.4.1
- Document accountability for all study drugs.

6.2.2.5 Criteria for Discontinuation of Study Treatment

Study Medication will be discontinued in the following instances

- Unacceptable toxicity, or toxicity that in the judgement of the investigator compromises the ability to continue study specific procedures or is considered to not be in the subject's best interest
- Subject request to discontinue for any reason
- Pregnancy during the study
- Development of active tuberculosis
- Discontinuation of the study at the request the IRB

Study medication may be discontinued in the following instances:

- Intercurrent illness that would in the judgement of the investigator affects assessments of clinical status to a significant degree. Following resolution of the intercurrent illness, the subject may resume study dosing at the discretion of the investigator.
- Lack of efficacy

Subject noncompliance

6.2.3 Post Study Care

After a subject has completed/terminated their participation in the study, long-term care for the subject will remain the responsibility of their primary treating provider.

6.2.4 Clinical Laboratory Assessments

Blood and urine samples will be collected throughout the study as outlined below, within Section 6.2, and also in Appendix 1 Study Procedure Table.

6.2.4.1 Blood Samples

Blood sample collection for the following:

- Chemistry profile: alkaline phosphatase, AST, ALT, total bilirubin, direct and indirect bilirubin, total protein, albumin, CPK, bicarbonate, blood urea nitrogen (BUN), chloride, creatinine, glucose, potassium, sodium
- Fasting glucose and lipid panel (total cholesterol, HDL, LDL, and triglycerides) at Day 1, Weeks 12, 24, 48.
 - If the patient is not fasting (no food or drinks except water for at least 8 hours prior to blood collection.
 - If the subject has not fasted prior to the visit, the visit may proceed but the subject must return within 72 hours in a fasted state to draw labs
- Hematology profile: complete blood count (CBC) with differential and platelet counts
- CD4+ cell count and percentage
- Plasma Quantitative HIV-1 RNA
- If no documented Hepatitis B immunity: Hepatitis B surface antigen, surface antibody and core antibody at Screening, Week 48.
 - The following tests will be conducted if the following criteria are met:
 - If positive surface antigen: plasma qualitative and quantitative HBV DNA, Hepatitis B virus e-antigen and antibody
 - If positive core antibody with negative surface antigen and surface antibody: plasma qualitative and quantitative HBV DNA, Hepatitis B virus e-antigen and antibody
- For subjects who are coinfected with Hepatitis B, plasma quantitative Hepatitis B DNA
- Hepatitis C Virus (HCV) antibody (subjects who are HCV antibody positive will have HCV RNA test performed) at Screening and Week 48.
- Plasma and serum storage sample for safety or virology testing (all visits except Screening Visit).

6.2.4.2 Urine samples

Urine samples will be collected for the following:

- Urinalysis
- Urine pregnancy testing (If positive at screening, subject will not be enrolled. If positive at subsequent visit, study medication will be discontinued)

6.2.5 Virologic Failure

Virologic failure is defined as virologic rebound or having HIV-1 RNA ≥ 50 copies/mL at study discontinuation or week 48

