2. STUDY OBJECTIVES

2.1. The primary objective of the study is:

To evaluate the proportion of participants with virologic failure determined by HIV-1 RNA ≥ 50 copies/mL at week 48 in virologically suppressed patients with HIV-1 infection switching from ATRIPLA® to BIKTARVY®.

2.2. The secondary objectives of the study are:

- To determine the safety of switching from ATRIPLA® to BIKTARV®Y in virologically suppressed
 patients with HIV-1 infection as determined by the proportion of participants with virologic failure, a
 rise in serum creatinine values, a change in lipid parameters, and change in CD4 cell count from
 baseline.
- To determine the efficacy of switching from ATRIPLA® to BIKTARVY® in virologically suppressed
 patients with HIV-1 infection as determined by the proportion of participants with HIV-1 RNA < 50
 copies/MI.
- To evaluate tolerability, durability of BIKTARVY® in virologically suppressed patients with the aid of 2 Patient Reported Outcomes (PRO) questionnaires (see appendix 3).

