6.2.5.1 Management of Viral Rebound

Subjects who meet either of the criteria listed below will be considered to have virologic rebound:

- At any post Day 1 Visit, an HIV-1 RNA ≥ 50 copies/mL which is subsequently confirmed at the following visit (scheduled or unscheduled)
- Any subject with HIV-1 RNA ≥ 50 copies/mL at study drug discontinuation

Following the unconfirmed virologic rebound, subjects will be asked to return to the clinic for a blood draw, 4 weeks after the date of the original test that had an RNA ≥50 copies/mL. If virologic rebound is confirmed

[figure not shown]
and the HIV-1 RNA is \geq 200 copies/mL, the blood sample from the confirmation visit will be the primary sample used for HIV-1 genotypic and phenotypic testing. After a subject's first post-baseline resistance test, additional testing will be conducted on a case-by-case basis. Any subject may be discontinued at Investigator's discretion or per local treatment guidelines.

If no resistance is detected from the genotype or phenotype, the subject may remain on study drug and HIV-1 RNA test should be again repeated 2-3 weeks later. If HIV-1 RNA \geq 50 copies/mL remains Investigators should carefully evaluate the risks and benefits of remaining on study drug and document this assessment in the on-site medical record.

Subjects who are nonadherent on an ongoing basis will be considered for discontinuation per the Investigator's discretion or local treatment guidelines. Sub-investigators who opt to discontinue study drugs for an individual subject must discuss with the Investigator prior to study drug discontinuation.

For subjects who are off study drug but remain in study, it will be the Investigator's discretion to manage virologic rebound.

Figure 1

6.2.5.2 Subjects with HIV-1 RNA ≥ 50 copies/mL at Study Drug Discontinuation or Week 48

Subjects with HIV-1 RNA \geq 50 copies/mL at Study Drug Discontinuation, last Visit, or Week 48 will be considered virologic failures. Subjects with HIV-1 RNA \geq 50 copies/mL at Week 48 will be asked to return for an unscheduled visit within 4 weeks for a retest as detailed in Section 6.2.5. Subjects with HIV-1 RNA \geq 200 copies/mL will also have resistance testing as detailed in Section 6.2.5.

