8.5.1.1 US FDA-defined Snapshot Algorithm

All HIV-1 RNA data collected on-treatment (i.e. including data collected up to 1 day after the last dose date of the study drug) will be used in the snapshot algorithm. Virologic outcome will be defined as the following categories:

- HIV-1 RNA < 50 copies/mL: subjects who meet this criteria by result of the last available ontreatment laboratory result in the Week 48 analysis window
- HIV-1 RNA ≥ 50 copies/mL: subjects who meet this criteria by result of the last available ontreatment laboratory result in the Week 48 analysis window or do not have laboratory results in the Week 48 window and who discontinue study drug either:
 - due to lack of efficacy or
 - for reason other than lack of efficacy and have the last available on-treatment HIV-1 RNA ≥ 50 copies/mL
- No virologic Data in the Week 48 Analysis Window: subjects who do not have on-treatment HIV-1 RNA data in the Week 48 window because
 - Discontinuation of the study drug for reason other than lack of efficacy and have the last available on-treatment HIV-1 RNA < 50 copies/mL or
 - Missing data during the Week 48 window but remain on study drug

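### The Section 2.2 safety objective names the proportion with virologic failure, but no endpoint or analysis reports that proportion under the protocol's own definition in 6.2.5

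*Combined protocol and SAP*

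**What the plan says.** **Objectives.** The primary objective (2.1) is "To evaluate the proportion of participants with virologic failure determined by HIV-1 RNA ≥ 50 copies/mL at week 48". The first secondary objective (2.2) concerns the safety of switching, "as determined by the proportion of participants with virologic failure" along with creatinine, lipid and CD4 changes. No criterion for failure is attached there.

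**Definition.** Section 6.2.5: "Virologic failure is defined as virologic rebound or having HIV-1 RNA ≥ 50 copies/mL at study discontinuation or week 48". Section 6.2.5.1 gives two routes to rebound: "At any post Day 1 Visit, an HIV-1 RNA ≥ 50 copies/mL which is subsequently confirmed at the following visit", and "Any subject with HIV-1 RNA ≥ 50 copies/mL at study drug discontinuation". Section 6.2.5.2 adds a value of 50 or more at the last visit.

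**Endpoints and analyses.** Sections 3.1, 8.1.1, 8.5.1 and 8.5.1.2 use the snapshot proportion with RNA ≥ 50 copies/mL. Sections 3.2, 8.1.2 and 8.5.2 add the snapshot proportion below 50. Under 8.5.1.1 the snapshot takes the last on-treatment result in the Week 48 window, with on-treatment ending 1 day after the last dose. One of its routes to the no-data category is "Missing data during the Week 48 window but remain on study drug". Neither 8.5 nor 8.6 contains an analysis of failure as 6.2.5 defines it.

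**The concern.** The protocol defines failure as something that can occur at any visit after Day 1 and is not undone by later re-suppression. The analysis looks at one window, on treatment. If 2.2 means failure as the protocol defines it, a stated safety objective ends the study without a result, and some subjects whom the protocol classes as failures appear in the tables only as suppressed or without data. In a descriptive single cohort of about 100 subjects, a few such cases would change how the switch reads.

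**Working it through.** The plan has no figure to reproduce: 4.3 and 8.8 give about 100 subjects with no rate, power or margin, and 8.5.1 calls the analysis descriptive. The check is therefore one of classification. Example histories were run through both rule sets.

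Inputs: the definitions in 6.2.5, 6.2.5.1 and 6.2.5.2; the snapshot rules and 1-day cut-off in 8.5.1.1; the discontinuation visit within 5 days of stopping (6.2.2.4); continued evaluation off drug (6.2.2.3); and the provision in 6.2.5.1 that a subject with rebound but no detected resistance may stay on drug.

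| History | 6.2.5 failure? | Snapshot |
|---|---|---|
| A. Rebound at Week 12, confirmed at Week 16, below 50 on drug at Week 48 | Yes | < 50 |
| B. Confirmed rebound, re-suppressed, then stopped for an adverse event with last value < 50 | Yes | No data |
| C. Rebound at Week 36, confirmed at Week 40, on drug, no Week 48 sample | Yes | No data |
| D. Stopped for an adverse event, last on-drug value < 50, RNA ≥ 50 at a discontinuation visit 5 days later | Yes | No data |
| E. Stopped while < 50, stayed in study, RNA ≥ 50 off drug at Week 48 | Yes | No data |
| F. RNA ≥ 50 on drug at Week 48 | Yes | ≥ 50 |
| H. Stopped for an adverse event, last on-drug value ≥ 50 | Yes | ≥ 50 |
| I. Stopped for lack of efficacy, last value < 50, no confirmed rebound | No | ≥ 50 |

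These results are the same with a Week 48 window of ±6 days (6.2.2.3) or ±6 weeks (an Appendix 1 footnote that appears to belong to Week 48; that link is an inference). One further history depends on the window. G: RNA ≥ 50 at Week 48 with a retest below 50 on drug 28 days later is ≥ 50 under ±6 days and < 50 under ±6 weeks.

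A to E are failures that the snapshot does not count. F and H agree. I runs the other way, so neither set contains the other.

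**Could the number surface elsewhere?** Section 8.3 promises listings for subjects who do not complete, but history A completes. Section 8.6.3 summarises selected laboratory data at scheduled visits, whereas confirmation may be unscheduled. Appendix 2 has no HIV-1 RNA row, so graded-abnormality tables cannot show it.

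**Size, on assumed counts.** Let n = 100, with 2 snapshot failures that are also 6.2.5 failures and k further subjects who fail only under 6.2.5. The proportion is (2 + k)/100. With x = 2 + k, the exact 95% limits are the 0.025 quantile of Beta(x, n − x + 1) and the 0.975 quantile of Beta(x + 1, n − x).

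- k = 0: 2% (0.2-7.0)
- k = 1: 3% (0.6-8.5)
- k = 3: 5% (1.6-11.3)
- k = 5: 7% (2.9-13.9)

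In the other direction, if one of the 2 were history I and k = 0, the 6.2.5 figure would be 1% (0.0-5.4).

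The chance of at least one subject of types A to E among 100 is 1 − (1 − p)^100. For an assumed p of 1%, 2% or 5% this is 63%, 87% or 99%.

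**The case against.** **The primary objective is sound.** A reader might infer that the primary endpoint fails to deliver its objective. It does not fail: 2.1 carries its own Week 48 criterion in the same sentence, and 3.1, 8.1.1 and 8.5.1 match it. The analysis sections never label the snapshot number virologic failure.

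**Section 2.2 might borrow the criterion of 2.1.** It follows directly, and 6.2.5 sits under study procedures, where it directs retesting and resistance testing. A management definition can properly coexist with a snapshot endpoint. This reading is possible, but it makes the safety measure a duplicate of the primary endpoint, and 6.2.5 remains the only formal definition of the term. Either way the text needs clarifying.

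**The values are not all lost.** Sections 8.2.3 and 8.6 take safety data to 30 days after the last dose, 8.3 lists data for non-completers, and the no-data category is itself visible. History D also needs a visit on days 2 to 5, a last on-drug value below 50 and a stop not due to lack of efficacy. All of this stands and narrows the number of subjects affected. It does not yield a failure proportion, and history A is still reported only as a success.

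**The direction is not fixed.** A reader might infer that the snapshot must understate failure. History I shows that it need not.

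**Conclusion.** The point holds for 2.2. Followed as written, the plan gives a stated safety measure no result under the protocol's own definition, and the snapshot cannot stand in for it, because histories A to E are reported as suppressed or as having no data. This rests on reading the term in 2.2 as 6.2.5 defines it.

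For 2.1 the fault is only that one term has two meanings. The documents do not support saying that the primary analysis is wrong or that a reported rate would necessarily be too low. The 6.2.5 proportion could be higher than the snapshot ≥ 50 proportion or, less likely, lower. The size is unknown. The range of 3% to 7% against 2% rests wholly on assumed counts, and its intervals overlap widely. No test or decision rule changes, since the analysis is descriptive.

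**What to change.** Keep the snapshot as the primary analysis, and make these changes.

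- **Sections 3.2, 8.1.2 and 8.5.2:** add the proportion of full analysis set subjects who meet the 6.2.5 definition of virologic failure through Week 48, with an exact 95% confidence interval, a listing by criterion and a cross-tabulation against snapshot category.
- **Terms for this analysis:** 6.2.5 refers to discontinuing the study, while 6.2.5.2 refers to discontinuing study drug and to the last visit. Reconcile these so that each criterion can be programmed, and report failures that rest on off-drug RNA separately.
- **Section 2.1:** replace the term virologic failure with HIV-1 RNA ≥ 50 copies/mL by snapshot, so that the term keeps one meaning.

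The cost is one extra table and a few wording changes. Appendix 1 already schedules HIV-1 RNA at every visit. The sponsor also accepts that a failure figure less favourable than the snapshot may be reported.

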6.2.5.1 Management of Viral Rebound

Subjects who meet either of the criteria listed below will be considered to have virologic rebound:

- At any post Day 1 Visit, an HIV-1 RNA ≥ 50 copies/mL which is subsequently confirmed at the following visit (scheduled or unscheduled)
- Any subject with HIV-1 RNA ≥ 50 copies/mL at study drug discontinuation

Following the unconfirmed virologic rebound, subjects will be asked to return to the clinic for a blood draw, 4 weeks after the date of the original test that had an RNA ≥50 copies/mL. If virologic rebound is confirmed

[figure not shown]
and the HIV-1 RNA is \geq 200 copies/mL, the blood sample from the confirmation visit will be the primary sample used for HIV-1 genotypic and phenotypic testing. After a subject's first post-baseline resistance test, additional testing will be conducted on a case-by-case basis. Any subject may be discontinued at Investigator's discretion or per local treatment guidelines.

If no resistance is detected from the genotype or phenotype, the subject may remain on study drug and HIV-1 RNA test should be again repeated 2-3 weeks later. If HIV-1 RNA \geq 50 copies/mL remains Investigators should carefully evaluate the risks and benefits of remaining on study drug and document this assessment in the on-site medical record.

Subjects who are nonadherent on an ongoing basis will be considered for discontinuation per the Investigator's discretion or local treatment guidelines. Sub-investigators who opt to discontinue study drugs for an individual subject must discuss with the Investigator prior to study drug discontinuation.

For subjects who are off study drug but remain in study, it will be the Investigator's discretion to manage virologic rebound.

Figure 1

6.2.5.2 Subjects with HIV-1 RNA ≥ 50 copies/mL at Study Drug Discontinuation or Week 48

Subjects with HIV-1 RNA \geq 50 copies/mL at Study Drug Discontinuation, last Visit, or Week 48 will be considered virologic failures. Subjects with HIV-1 RNA \geq 50 copies/mL at Week 48 will be asked to return for an unscheduled visit within 4 weeks for a retest as detailed in Section 6.2.5. Subjects with HIV-1 RNA \geq 200 copies/mL will also have resistance testing as detailed in Section 6.2.5.

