6.2.2.3 Treatment Assessments (Week 4-48)

The following evaluations are to be completed at Weeks 4, 8, 12, 24, 36, and 48.

Study visits are to be completed within ± 2 days of the protocol specified visit date (based on the Day 1 visit) through Week 12, visits for Week 12, 24, 36 and 48 should be completed ± 6 days of the protocol specified date. If the subject is not evaluated within the visit window, the database will reflect missing/no available data for that visit.

Regularly scheduled evaluations will be made on all the subjects, even if they no longer are receiving study drug.

The following will be completed at each visit:

- Subject will read PRO questionnaires (appendix 3) to themselves and write/mark answers directly onto questionnaire.
- Review/record of SAE/AE's and changes in concomitant medications

- Obtain measurements of blood pressure, pulse, temperature, height and weight
- Complete or symptom directed physical exam, as clinically indicated
- Subjects will be reminded of the importance of adherence and taking the study medication at the same time each day
- Obtain blood and urine samples as described in section 6.2.4.1
- Document dispensing of study drug and accountability for all study drugs.
- Subjects should be reminded of the importance of adherence and taking the study medication at the same time each day.
- Record all AE/SAE's to any protocol mandated procedures
- Subjects who meet criteria for virologic failure will be managed according to the Management of Virologic Rebound Section 6.2.5.

A prescription will be provided for continuation of antiviral therapy at the final study appointment. The subject will receive an additional 7 day supply of the study drug to prevent lapse in therapy.

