8.1.1 Primary Endpoint

The primary efficacy endpoint is the proportion of subjects that have HIV-1 RNA ≥ 50 copies/mL at week 48, as defined by the FDA snapshot analysis.

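### Only subjects at or above 50 copies/mL at Week 48 have a planned retest, and the snapshot rule lets a later in-window, on-treatment value replace the failure

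*Combined protocol and SAP*

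**What the plan says.** The primary endpoint is stated in Section 8.1.1: "The primary efficacy endpoint is the proportion of subjects that have HIV-1 RNA ≥ 50 copies/mL at week 48", by the FDA snapshot. Section 8.5.1.1 assigns both the below-50 and the at-or-above-50 categories from the "last available ontreatment laboratory result in the Week 48 analysis window". On-treatment data are limited to those collected while on study drug, "including data collected up to 1 day after the last dose date of the study drug". The section gives no day limits for the analysis window and does not mention unscheduled or confirmatory samples.

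Section 6.2.5.2 covers subjects at or above 50 at drug discontinuation, "last Visit, or Week 48 will be considered virologic failures", and attaches no retest condition to that label. It then says that those at or above 50 at Week 48 "will be asked to return for an unscheduled visit within 4 weeks for a retest", following Section 6.2.5. Section 6.2.5.1 puts the confirmatory draw "4 weeks after the date of the original test that had an RNA ≥50 copies/mL". The Appendix 1 schedule has no column after Week 48 other than early discontinuation.

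Two visit windows are given for Week 48. Section 6.2.2.3 has ±6 days and adds that a subject seen outside the window is recorded as missing for that visit. Appendix 1 carries a ±6 weeks footnote. Its marker is lost in the extracted text, but it appears to belong to Week 48, because the other two footnotes are assigned to other columns. On drug supply after the last visit, Section 6.2.2.3 says: "The subject will receive an additional 7 day supply of the study drug to prevent lapse in therapy". It also provides a prescription for continued antiviral therapy.

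**The concern.** Taking the latest value in a window does no harm when the number of samples per subject does not depend on the result. Here it does: a second Week 48 measurement is planned only for those whose first one was a failure. A rule that then prefers the later value can remove failures from the primary count, while the schedule offers no matching chance to remove successes. The primary proportion would fall, and the secondary below-50 proportion would rise by the same amount.

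With about 100 subjects and a purely descriptive primary analysis, the result may rest on a handful of failures, so reclassifying one or two shows in the headline figure. The report could also contain subjects who are virologic failures under Section 6.2.5.2 and successes under Section 8.5.1.1.

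**Working it through.** The plan states no expected failure rate, re-suppression rate or precision target, so there is no figure of its own to reproduce. The check has three parts.

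**1. Is the retest in the window?** Let v be the day of the Week 48 visit relative to its nominal date, L the days from that visit to the retest (1 to 28), and W the half-width of the window. The retest is inside if |v + L| ≤ W. The visit windows stand in for the undefined analysis window.

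- W = 42 days (±6 weeks): v + 28 ≤ 42 gives v ≤ 14. Every retest on days 1–28 is inside if the visit is no more than 14 days late.
- W = 6 days: an on-time visit (v = 0) allows L ≤ 6. A visit 6 days early allows L ≤ 12. A visit 6 days late allows none. A day-28 retest would need v ≤ −22, which the visit window does not permit.

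**2. Is it on treatment?** If the 7-day supply is the last study drug, on-treatment data end at about 7 + 1 = 8 days after the visit, so L ≤ 8. A draw at exactly 4 weeks then fails under either window. If study drug continues to the retest, this limit falls away.

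**3. Effect on the reported rate.** Reported rate = p × (1 − r × f), where:

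- p = proportion at or above 50 at the scheduled draw;
- r = proportion of those below 50 on retest;
- f = share of retests that are both in the window and on treatment.

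All three are assumptions. With p = 3%, r = 0.5, and retest days spread evenly over days 1–28 unless stated:

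| Reading of the text | Days that count | f | Reported rate |
|---|---|---|---|
| ±6 weeks, study drug continues to the retest | 1–28 | 1 | 3% × (1 − 0.5) = 1.5% |
| ±6 weeks, 7-day supply is the last drug | 1–8 | 8/28 | 3% × (1 − 0.143) = 2.6% |
| ±6 days, visit on time | 1–6 | 6/28 | 3% × (1 − 0.107) = 2.7% |
| ±6 days, visit 6 days late | none | 0 | 3.0% |
| All retests at exactly 4 weeks, 7-day supply is the last drug | none | 0 | 3.0% |

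The relative reduction is r × f and does not depend on p. For r from 0.3 to 0.7 it is 30–70% when all retests count, and 0.3 × 8/28 to 0.7 × 8/28, or about 9–20%, when only the first 8 days count. In an illustrative 100 subjects, 3 failures (exact 95% CI 0.6 to 8.5%) would become 1 (0.0 to 5.4%) if two retests below 50 replaced the scheduled values.

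**The case against.** The strongest reply is that the plan's own timing may exclude most or all retests. Section 6.2.5.2 refers to 6.2.5, where the draw is set at 4 weeks. The final supply is 7 days and only 1 day after the last dose counts as on treatment. Section 6.2.2.3 separates the continuation prescription from study drug, and Appendix 1 shows no dispensing at Week 48. On that reading, the effect is nil. If the analysis window follows ±6 days, it is small at most. This stands, and it limits the size. It does not settle the matter: 6.2.5.2 itself allows any day within 4 weeks, 6.2.5.1 allows a subject without resistance to stay on study drug, and the documents do not say whether prescribed drug counts.

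A reader might infer that the primary rate is certain to be biased downward, or that no subject could ever move from success to failure. The documents support neither. The first depends on the unresolved readings above. The second holds for draws planned after a Week 48 value below 50, but unscheduled samples are not barred. Under ±6 weeks (weeks 42 to 54), a repeat following a Week 36 rebound could fall at about weeks 41 to 44, after an early Week 48 visit.

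Two further replies have some force. No test or margin turns on the result, and one or two subjects lie well within sampling error at this size. Also, the latest-in-window rule is part of the algorithm that the plan adopts, and Section 1.1 wants comparability with a Phase 3 switch study. The rule is not an error in itself; the difficulty is its pairing with sampling triggered by the outcome.

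**Conclusion.** The point holds in a conditional form. As written, a retest planned only for Week 48 failures can, if in the window and on treatment, replace the failure with a success in the primary endpoint and contradict Section 6.2.5.2. The direction of any effect from this planned retest is settled by the text: it can only lower the failure rate. The size is not settled. It runs from nil to a halving under the assumed 50% re-suppression: 3% falls to about 2.6% if retests on days 1–8 count and to 1.5% if all do. These figures rest on assumed failure and re-suppression rates, on evenly spread retest days, and on using the visit windows for the undefined analysis window. The point deserves correction before analysis because it touches the primary endpoint and is cheap to remove.

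**What to change.** Add to Section 8.5.1.1 that, where a scheduled on-treatment Week 48 result exists, it determines the snapshot category, and that retests triggered by Section 6.2.5 do not replace it. The words *on-treatment* are needed because Section 6.2.2.3 keeps evaluating subjects who have stopped study drug.

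In addition:

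- state the Week 48 analysis window in days, and reconcile ±6 days in Section 6.2.2.3 with ±6 weeks in Appendix 1;
- reconcile the retest timing in Section 6.2.5.2 with that in 6.2.5.1;
- report retests separately, as confirmed or not confirmed;
- give the latest-in-window snapshot as a sensitivity analysis, so that comparison with other snapshot results is kept.

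The analysis rule needs no new data. Its cost is that the reported failure rate may be slightly higher and the primary rule departs slightly from latest-in-window.
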